## 4 Endpoints and Assessment Methods

### 4.1 Primary Endpoints and Assessment Methods

See Section 9.1 of the protocol.

### 4.2 Secondary Endpoints and Assessment Methods

See Section 9.2 of the protocol.

### 4.3 Observational Endpoints and Assessment Methods

See Section 9.3 of the protocol.

### 4.4 Derived Endpoints: Calculation Methods

#### 4.4.1 Safety

##### 4.4.1.1 Solicited Reactions

###### 4.4.1.1.1 Daily Intensity

All daily records for solicited reactions will be derived into daily intensity according to the following classification: None, Grade 1, Grade 2, Grade 3, or Missing.

For the derivation of daily intensities the following sequential steps will be applied:

- 1) Solicited reactions (except Fever) with an investigator presence recorded as “No” and with all daily records missing then all daily intensities will be derived as None.

- 2) For a temperature partially missing after decimal point, the data will be analyzed replacing “MD” (missing data) by zero. For example, a “39.MD” daily temperature will be considered as “39.0°C” at the time of analysis.
- 3) For non-measurable solicited reactions, daily intensities will correspond to daily records reported in the clinical database. For measurable solicited reactions the daily measurements reported in the clinical database will be converted based upon the intensity scales defined in the protocol; this assumes a reaction that is too large to measure (non measurable, “NM”) is Grade 3. Note the intensity could be considered “None” (not a reaction) in the analysis despite being considered a reaction by the investigator (e.g., swelling measurement  $> 0$  mm but  $< 25$  mm in adults).

Note: The maximum intensity on the ongoing period is derived from the record of the maximum intensity/measurement after the end of the solicited period following the rule described above.

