**Table 9.1: Solicited injection site reactions: terminology, definitions, and intensity scales**

CRF term (MedDRA lowest level term [LLT])	Injection site tenderness	Injection site erythema	Injection site swelling
Diary card term	Tenderness	Redness	Swelling
Definition		Presence of a redness including the approximate point of needle entry	Swelling at or near the injection site Swelling or edema is caused by a fluid infiltration in tissue or cavity and, depending on the space available for the fluid to disperse, swelling may be either soft (typically) or firm (less typical) to touch and thus can be best described by looking at the size of the swelling
Intensity scale*	Grade 1: Minor reaction when injection site is touched  Grade 2: Cries or protests when injection site is touched  Grade 3: Cries when injected limb is moved, or the movement of the injected limb is reduced	Grade 1: > 0 to < 25 mm  Grade 2: $\geq 25$ to < 50 mm  Grade 3: $\geq 50$ mm	Grade 1: > 0 to < 25 mm  Grade 2: $\geq 25$ to < 50 mm  Grade 3: $\geq 50$ mm

\* For the subjective reaction of tenderness, parents / guardians will record the intensity level (Grade 1, 2, or 3) in the diary card. For the measurable reactions of redness and swelling, they will record just the size of the reaction, and the classification as Grade 1, 2, or 3 will be assigned at the time of the statistical analysis.

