# 11 Data Collection and Management

## 11.1 Data Collection and CRF Completion

Individual safety diary cards, specifically designed for this trial by the Sponsor and provided to the study sites, will be given to study participants for the recording of daily safety information as described in [Section 9.3.2.3](#). These diary cards will include prelisted terms and intensity scales (see [Table 9.1](#) and [Table 9.2](#)) as well as areas for free text to capture additional safety information or other relevant details. Parents or guardians will also be provided with rulers for measuring the size of injection site reactions, and with standard digital thermometers for measuring daily temperatures. To ensure consistency of reporting, the study sites will instruct parents / guardians on how to correctly use these tools.

At specified intervals, the Investigator or an authorized designee will interview the parents / guardians to collect the information recorded in the diary card, and will attempt to clarify anything that is incomplete or unclear. All clinical trial information gathered by the study site will be reported electronically by the Investigator or authorized designee using a web-based CRF. (Any information that was not documented in the diary card will first be captured in the source document and then reported electronically.) The CRF has been designed specifically for this trial under the responsibility of the Sponsor, using a validated Electronic Records / Electronic Signature-compliant platform (21 CFR Part 11).

To ensure the correct and consistent completion of the CRFs, the Sponsor or authorized representative will provide all necessary tools, instructions, and training to all site staff involved in data entry prior to study start. Additional instructional documents such as training manuals and completion guidelines will be provided to assist with data entry during the course of the trial.

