## 12.3 Handling of Missing Data and Outliers

### 12.3.1 Safety

No replacement will be done. Missing safety data will not be replaced. All subjects with safety data and all safety data recorded in the CRFs will be included in the safety analyses. No search for outliers will be performed during the statistical analysis.

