#### **4.4.1.1.3 Presence**

Presence is derived from the maximum overall intensity on the period considered:

- None: No presence
- Grade 1, Grade 2, or Grade 3: Presence
- Missing: Missing presence

Subjects with at least one non-missing presence for a specific endpoint will be included in the analysis. Conversely, those without a non-missing presence will not be included in the analysis of the endpoint.

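### For the eight non-fever solicited reactions, with no daily records an investigator's No counts as a non-reactor while a Yes drops out, so any such Yes lowers the reported rate

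*SAP*

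**What the plan says.** SAP 4.4.1.1.1 derives daily intensities in sequential steps. Step 1 applies to every solicited reaction except fever. Where the investigator's presence field is No "and with all daily records missing then all daily intensities will be derived as None". Step 3 takes everything else from the daily data: "For non-measurable solicited reactions, daily intensities will correspond to daily records reported in the clinical database", and measurable reactions are graded from the daily measurements. The investigator's presence field appears in no other step.

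SAP 4.4.1.1.3 then states that "Presence is derived from the maximum overall intensity on the period considered". A Missing maximum gives a Missing presence, and "those without a non-missing presence will not be included in the analysis of the endpoint".

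SAP 5.3.1.4 sends missing solicited intensities back to 4.4.1.1.1, so no further rule is found there. Protocol 12.3.1 says that missing safety data are not replaced and that "All subjects with safety data and all safety data recorded in the CRFs will be included in the safety analyses". SAP 5.3.1 repeats the no-replacement principle.

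**The concern.** Two children with the same data gap are handled differently according to the investigator's answer. With No, the child stays in the denominator as a non-reactor. With Yes, the child disappears from that endpoint. The SAP does not state this second outcome in words; it follows from presence being built only on intensity.

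The SAP's reason for letting measurement override the investigator does not help here. Its example is a swelling below 25 mm in adults, which the analysis may class as no reaction. In this toddler protocol, Table 9.1 starts redness and swelling at "Grade 1: > 0 to < 25 mm". Tenderness and the five non-fever systemic reactions in Table 9.2 also have a Grade 1 at the mildest form of the symptom. A Yes therefore cannot grade down to None, and in the case at issue there is no measurement to override it.

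SAP section 1 gives as a purpose of the trial that safety is comparable when MenACYW is given alone and concomitantly, and the trial is open-label. A rule that can only lower a rate, and by an amount that depends on how many such records each group has, is unhelpful for that description. It also fits poorly with the protocol's commitment to include all recorded safety data.

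**Working it through.** **Which reactions.** Table 9.1 lists 3 injection-site reactions and Table 9.2 lists 6 systemic reactions. Step 1 exempts fever, so 3 + 5 = 8 of the 9 are affected.

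**No figure to reproduce.** The documents give neither an expected reaction rate nor a missing-record rate.

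**Notation, per group and reaction.**
- A: children with daily records, of whom E have the reaction
- B: no daily records, investigator No
- C: no daily records, investigator Yes
- n = A + B + C

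**Formulas.**
- SAP rate = E/(A + B)
- Rate if the Yes is counted = (E + C)/n
- Since E = SAP rate × (n − C), the SAP rate minus the counted rate = −(1 − SAP rate) × C/n

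**Inputs.** Planned group sizes of 50, 100 and 200 come from SAP 3.2. Everything else is assumed: B about 5% of the group, C from 0 to 5%, and a rate of 10%, 30% or 50% among children with daily records.

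| n | Assumed rate | B | C | A | E | SAP rate | Yes counted | Shift (points) |
|---|---|---|---|---|---|---|---|---|
| 200 | 30% | 10 | 0 | 190 | 57 | 57/200 = 28.5% | 57/200 = 28.5% | 0.00 |
| 200 | 30% | 10 | 2 | 188 | 56 | 56/198 = 28.3% | 58/200 = 29.0% | −0.72 |
| 200 | 30% | 10 | 4 | 186 | 56 | 56/196 = 28.6% | 60/200 = 30.0% | −1.43 |
| 200 | 30% | 10 | 10 | 180 | 54 | 54/190 = 28.4% | 64/200 = 32.0% | −3.58 |
| 200 | 10% | 10 | 10 | 180 | 18 | 18/190 = 9.5% | 28/200 = 14.0% | −4.53 |
| 100 | 30% | 5 | 2 | 93 | 28 | 28/98 = 28.6% | 30/100 = 30.0% | −1.43 |
| 50 | 30% | 2 | 1 | 47 | 14 | 14/49 = 28.6% | 15/50 = 30.0% | −1.43 |

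Formula check on the third row: (1 − 0.2857) × 4/200 = 0.0143.

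**Scale.** Over all three assumed rates and all three group sizes, C at 1% to 2% of the group (at least one child) shifts the rate by about 0.5 to 1.8 points. The Clopper-Pearson 95% half-widths are about 4 to 7 points at n = 200, 6 to 10 at n = 100 and 9 to 15 at n = 50. With C at 5% and n = 100 or 200, the shift is about 2.6 to 4.5 points. At a 10% rate and n = 200 it slightly exceeds the half-width (4.53 against 4.4).

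**Between groups.** With C = 4 of 200 in one group and C = 2 of 100 in another, both at 30%, the shifts are equal and cancel. With C = 4 of 200 against none, a spurious gap of 1.43 points remains.

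**The No step itself.** In the first row, counting the ten No children gives 57/200 = 28.5%, which is right if those answers are right. Dropping them would give 57/190 = 30.0%, which is too high. The fault lies in the missing counterpart, not in step 1.

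**The case against.** The strongest reply is that the case may hardly occur. Protocol 11.1 has the investigator interview parents and clarify incomplete entries, and "Any information that was not documented in the diary card will first be captured in the source document and then reported electronically". Protocol 13.2 has missing diary data clarified verbally and transferred to the CRF, and 11.2 applies consistency checks and queries. All of this works against a Yes with nothing behind it, and that part of the reply stands. It does not remove the case. The diary is reviewed 30 to 44 days after vaccination, when a parent may confirm redness but be unable to give millimetres for each of days 0 to 7.

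A reader might also infer that step 1 is about blank diaries, and so relies on recall only when recall is negative. The SAP speaks of daily records, not of diaries. Those fields may be empty simply because the site ticked No, in which case step 1 restores true non-reactors. The fever exemption fits that reading, since temperature is recorded daily regardless. The documents do not show the CRF layout, so neither reading can be established.

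Safety is an observational, descriptive objective without hypotheses, so no formal conclusion turns on this. That limits the weight of the point. It does not make the rule right when the case occurs.

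**Conclusion.** The one-sided handling is in the SAP text. It can only lower a non-fever solicited rate, by (1 − SAP rate) × C/n, relative to counting the recorded Yes. Reading that as bias assumes that the Yes is correct. The effect is zero for any group and reaction with no such case. On the assumed range of 1% to 2% it is small beside the sampling error. The change is still worth making, because the rule gives a wrong rate whenever the case arises.

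Two stronger readings are tempting and are not supported:
- **That every non-fever rate is biased downward.** This would need at least one such Yes in every group for each of the eight reactions. The documents give no count, and their clarification procedures work against it.
- **That the loss is largest where the reaction is more common.** Suppose a share m of children lack daily records, independently of reaction, and the true rate is r. The loss is then rm(1 − r)/(1 − rm). At m = 10% it is 0.016/0.98 = 1.6 points at r = 20%, 0.025/0.95 = 2.6 at 50% and 0.009/0.91 = 1.0 at 90%. It rises and then falls.

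**What to change.** Keep the No step. Add to SAP 4.4.1.1.1 and 4.4.1.1.3: *for solicited reactions other than fever, if investigator presence is Yes and all daily records are missing, presence is Yes, and intensity, time of onset and number of days of occurrence are Missing.* Count the child in numerator and denominator for occurrence, and show a grade-missing row in the intensity tables.

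Also:
- Report the number of such cases by group and reaction, so that the reader can see whether the issue arose at all.
- Align SAP 4.4.1.4.6, which requires at least Grade 1 for a reaction leading to discontinuation and so would miss an ungraded one.
- State in SAP 5.3.1 that step 1 is an exception to the no-replacement principle there and in protocol 12.3.1.

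This matches the SAP's own practice for unsolicited non-serious events. There an event with a verbatim term is kept unless it is Grade 0 (4.4.1.2.1), a missing onset stays in the tables (4.4.1.2.4) and a missing intensity stays missing (5.3.1.4).

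The cost is a few sentences and some programming, because presence without a grade must be carried through onset, days of occurrence and the discontinuation tables. A few reactions would be counted without grade or onset. If no such case occurs, the results do not change.

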#### **4.4.1.1.2 Maximum Overall Intensity**

Maximum overall intensity is derived from the daily intensities computed as described in [Section 4.4.1.1.1](#) and is calculated as the maximum of the daily intensities over the period considered.

#### **4.4.1.1.3 Presence**

Presence is derived from the maximum overall intensity on the period considered:

- None: No presence
- Grade 1, Grade 2, or Grade 3: Presence
- Missing: Missing presence

Subjects with at least one non-missing presence for a specific endpoint will be included in the analysis. Conversely, those without a non-missing presence will not be included in the analysis of the endpoint.

#### **4.4.1.1.4 Time of Onset**

Time of onset is derived from the daily intensities computed as described in [Section 4.4.1.1.1](#). It corresponds to the first day with intensity of Grade 1, Grade 2, or Grade 3.

Note: If a reaction is not continuous (i.e., reaction occurs over two separate periods of time intervened by at least one daily intensity Missing or None) then the time of onset is the first day of the first occurrence.

#### **4.4.1.1.5 Number of Days of Occurrence**

Number of days of occurrence over the period considered is derived from the daily intensities computed as described in [Section 4.4.1.1.1](#). It corresponds to the number of days with daily intensities of Grade 1, Grade 2, or Grade 3. Number of days of occurrence on the solicited period with a specified intensity may also be derived.

#### **4.4.1.1.6 Overall Number of Days of Occurrence**

If a reaction is ongoing at the end of the solicited period, then the overall number of days of occurrence is derived from the daily intensities and the stop date of the reaction after the end of the solicited period. The overall number of days of occurrence is:

- (stop date – last vaccination date) + (number of days of occurrence within the solicited period) – length of the solicited period + 1

If the stop date is missing or incomplete (contains MD), the overall number of days of occurrence will be considered as Missing.

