**9.3.2.3.3 Unsolicited Non-serious Adverse Events From Day 0 to Day 30 After Vaccination**

In addition to recording solicited reactions, parents / guardians will be instructed to record any other medical events that may occur during the 30-day period after vaccination. Space will be provided in the diary card for this purpose.

For each unsolicited non-serious AE, the following information is to be recorded:

- Start and stop datesa
- Intensity of the event:
  - For measurable unsolicited non-serious AEs that are part of the list of solicited reactions, the size of the AE as well as the temperature for fever will be collected and analyzed based on the corresponding scale used for solicited reactions (see [Table 9.1](#) and [Table 9.2](#))
  - Other unsolicited non-serious AEs will be classified according to the following intensity scale:
    - Grade 1: No interference with activity
    - Grade 2: Some interference with activity
    - Grade 3: Significant; prevents daily activity
- Action taken for each AE, if any (e.g., medication)

The action taken by the subject / guardian to treat any **unsolicited AEs** will be classified in the CRF using the following scale:

0: None

1: Medication (self-medication with an existing prescription or over-the-counter medication)

2: Health care provider contact (no new medication prescribed)

---

a The stop date of all related AEs will be actively solicited. For other events, the investigator will provide the stop date when it becomes available. AEs for which no stop date was obtained during the course of the trial will be considered as ongoing at the end of the trial.

3: Health care provider contact and prescription of a new medication (health care provider instructed subject to take a new medication, either an over-the-counter medication or one requiring a written prescription)

- Whether the AE led to discontinuation
- Whether the AE was related to vaccination (for unsolicited systemic AEs)

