#### **4.4.1.1.7 Ongoing**

Ongoing is derived from the last daily intensity of the solicited period computed as described in Section 4.4.1.1.1 and the maximum intensity on the ongoing period. The investigator's ongoing flag is not used because the measurement would determine the ongoing status of the reaction. Note the intensity could be considered None (not a reaction) in the analysis despite being considered a reaction by the investigator (e.g., swelling measurement  $> 0$  mm but  $< 25$  mm in adults). If the last daily intensity of the solicited period is at least Grade 1 and maximum intensity on the ongoing period is also at least Grade 1, then the reaction is considered ongoing. In any other cases the reaction will not be considered as ongoing.

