#### 4.4.1.2.5 Duration

Duration is derived from the start and stop dates of the unsolicited non-serious AE provided in the clinical database:

- stop date of unsolicited non-serious AE - start date of unsolicited non-serious AE + 1.

The duration should be considered as missing only if one or both of the start and stop dates of the unsolicited non-serious AE is missing or partially missing.

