#### 4.4.1.3.3 Duration

Duration will be computed using the same methodology as for unsolicited non-serious AEs described in [Section 4.4.1.2.5](#).

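### Unsolicited AEs and SAEs without a stop date get a Missing duration (solicited reactions: only the overall day count), so ongoing events are merged with unknown dates and the remaining durations lean short

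*SAP*

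**What the plan says.** **Solicited reactions.** SAP 4.4.1.1.6 builds an overall number of days for a reaction still present at the end of the solicited period, using its stop date. Then: "If the stop date is missing or incomplete (contains MD), the overall number of days of occurrence will be considered as Missing". Two neighbouring derivations need no stop date. The count within the solicited period (SAP 4.4.1.1.5) comes from the daily grades: "It corresponds to the number of days with daily intensities of Grade 1, Grade 2, or Grade 3". The ongoing status (SAP 4.4.1.1.7) comes from the last daily grade and the maximum intensity afterwards.

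**Unsolicited non-serious AEs.** SAP 4.4.1.2.5: "The duration should be considered as missing only if one or both of the start and stop dates" is absent or partial.

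**SAEs.** SAP 4.4.1.3.3: "Duration will be computed using the same methodology as for unsolicited non-serious AEs".

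**Status in the protocol.** A footnote to Protocol 9.3.2.3.3, the section on unsolicited non-serious AEs, says: "AEs for which no stop date was obtained during the course of the trial will be considered as ongoing" when the trial ends.

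**Where the values are used.** Protocol 9.3.2.2 lists duration as an endpoint for unsolicited AEs and SAEs, and number of days of occurrence for solicited reactions up to 7 days after vaccination. SAP Table 5.2 lists duration for all of these. Protocol 12.3.1 and SAP 5.3.1.5 rule out replacing missing safety data or imputing stop dates.

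**The concern.** An event still present at the last contact is not an event about which nothing is known. Its start is known, its status is known, and its duration is at least the time observed. The SAP turns this into the same Missing value that it gives to an event whose dates were never properly recorded.

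Whether a duration exists then depends partly on how long the event lasted, because an event that outlasts follow-up is more likely to have no stop date. A summary of the non-missing durations therefore leans short. At stake is the description of persistence, mainly for unsolicited AEs and SAEs, where the SAP derives no second measure to fall back on.

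**Working it through.** **Inputs.** The solicited period is D0 to D07 (SAP 3.2), which I take as L = 8 days because SAP 4.4.1.1.6 does not give the number. Visit 2 is D30 to D44 (Protocol 5.1.1). Unsolicited AEs are analysed with onset from day 0 to day 30 (SAP 4.4.1.2.4). No event durations appear in either document, so those below are assumed.

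**1. The formula when a stop date exists.** With stop day S counted from vaccination and d graded days within the period, the overall count is S + d − L + 1.
- Every day graded, stop on D10: 10 + 8 − 8 + 1 = 11.
- Every day graded, stop on D30: 30 + 8 − 8 + 1 = 31.
- Graded on D5 to D7 only, stop on D10: 10 + 3 − 8 + 1 = 6.

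All three equal the inclusive calendar count, so the formula is sound.

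**2. What is known when there is no stop date.**
- An unsolicited AE that starts on D20 and is present at Visit 2 on D37 has lasted at least 37 − 20 + 1 = 18 days. The SAP value is Missing.
- A solicited reaction graded every day, still present on D37 and with no stop date ever obtained, has lasted at least 37 + 8 − 8 + 1 = 38 days. The overall count is Missing, but the D0–D07 count of 8 and the ongoing status remain. That status means ongoing past the solicited period, not at trial end. A reaction stopping on D9 (9 + 8 − 8 + 1 = 10 days) has the same D0–D07 count and the same status.

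**3. Effect on a percentage table.** SAP Table 5.1 presents clinical safety results as numbers and percentages. Assume 100 AEs, of which 95 resolve in under 30 days and 5 are ongoing after at least 30 days. Among non-missing durations, 0/95 = 0% last 30 days or more. With a separate ongoing category the figure is 5/100 = 5%.

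**4. How often it could happen.** This is a simulation of 1,000,000 events per row. Onset is uniform over D0–D30, and durations are exponential, rounded up to whole days. Every event that passes Visit 2 is assumed to have no stop date, so the active pursuit of stop dates described in the protocol is ignored.

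| Assumed mean before rounding (days) | Visit 2 | Missing | Mean, all events | Mean, non-missing | Longest tenth Missing | Missing events outside longest tenth |
|---|---|---|---|---|---|---|
| 3 | D30 | 8.2% | 3.5 | 3.2 | 27.5% | 54.4% |
| 3 | D44 | 0.1% | 3.5 | 3.5 | 0.5% | 0.0% |
| 7 | D30 | 20.8% | 7.5 | 5.6 | 70.3% | 65.6% |
| 7 | D44 | 2.8% | 7.5 | 6.9 | 27.3% | 1.8% |
| 14 | D30 | 38.7% | 14.5 | 7.7 | 100.0% | 73.8% |
| 14 | D44 | 14.3% | 14.5 | 10.4 | 84.4% | 39.6% |
| 21 | D30 | 51.0% | 21.5 | 8.7 | 100.0% | 80.1% |
| 21 | D44 | 26.2% | 21.5 | 12.1 | 100.0% | 61.1% |

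The shift is downward in every row but one, where it is nil to one decimal. Long events are over-represented among the Missing, but with Visit 2 at D30 more than half of the Missing events lie outside the longest tenth, because late onset also leaves an event open. The means show direction only; the SAP plans no mean duration.

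**The case against.** A reader might infer that the longest solicited reactions vanish from the duration results. The documents do not support that. The protocol endpoint is confined to the 7 days after vaccination, and the D0–D07 count serves it without a stop date. The same footnote in Protocol 9.3.2.3.3 says stop dates of related AEs are actively sought, and Protocol 9.3.2.3.6 treats all injection site and solicited systemic reactions as related. Protocol 5.1.4 requires follow-up of unresolved related events until they have resolved or reached a stable or chronic state. The reaction still present on D37 would therefore normally acquire a stop date later. This stands, and it leaves mainly unrelated AEs and SAEs, plus events that become stable or chronic and may never have a stop date. Under Protocol 5.2.12 no further safety information is sought after loss to follow-up.

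A reader might also infer that Missing durations are deleted from the tables. The SAP does not say so; they may appear as a row. Even then, the row would mix ongoing events with incomplete dates and hide the known minimum. The events themselves stay in the counts, and SAE outcome is summarised separately.

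Nor is this a flat contradiction between the documents. Ongoing is a status and Missing is a value, and both can be true of one event. The footnote sits in the unsolicited non-serious section, and its reach to SAEs and solicited reactions is not stated. For those, the point rests on informative missingness alone.

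**Conclusion.** The point holds in a limited form. For unsolicited AEs and SAEs, and for the overall day count of solicited reactions, the SAP does not separate an event known to be ongoing from one with unknown dates. Summaries of the non-missing values lean short. The events affected are disproportionately long or late in onset; it would be too strong to say that they are the longest.

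The size cannot be derived from the documents. Under the assumptions above, the Missing share runs from 0.1% to 51.0%, depending on typical duration and the Visit 2 date. Active pursuit of stop dates for related events should reduce it. Severity is minor: safety is a descriptive objective, and incidence, intensity and relatedness results do not change.

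**What to change.** In SAP 4.4.1.1.6, 4.4.1.2.5 and 4.4.1.3.3, add that an event with a known start date that is ongoing at last contact is tabulated in a separate, flagged category, *ongoing, at least x days*:
- For unsolicited AEs and SAEs, x = last contact date − start date + 1.
- For solicited reactions, x is the existing overall formula with last contact date in place of stop date.

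Name the data field that establishes ongoing status at last contact for each event type. Keep Missing for incomplete dates and unknown status. Do not impute stop dates, full or partial: the category reports observed time as a minimum and so stays within Protocol 12.3.1 and SAP 5.3.1.5.

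The cost is SAP wording, programming and one extra category in the duration tables. No new data collection is proposed.
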